5.2 Efficacy Evaluations

These are the measures that will be used to assess the efficacy of the study intervention

Aim 1: N/A

Aim 2: N/A

Aim 3: The primary efficacy outcome is the difference in change in self-efficacy between baseline and six-month visits for the intervention group versus control, as measured by the modified Generalized Self-Efficacy Scale.

5.2.1 Diagnostic Tests, Scales, Measures, etc.

See the list of CASIs in section 5.1.3.1 above.

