6.3.2 Analysis

Aim 1: We will conduct a deductive qualitative analysis of focus group transcripts and in-depth interview transcripts with our theoretical model guiding the coding process. Codes related to model constructs will be assigned to interview segments to organize the data, using the software NVivo, with two study team members separately reviewing the first 10 transcripts line by line, assigning codes as concepts become apparent. We will compare text segments to those that have been previously assigned the same code, and to segments coded separately by each analyst, to decide whether they reflect the same concept. We will use this process to generate a coding scheme, then apply it to all transcripts. Once coding is complete, we will review the data to document emerging themes-general insights gleaned from the entirety of the data- which may inform intervention content.

Aim 2: Survey data will be summarized via descriptive statistics. We will set a >80% threshold for high acceptability, feasibility and appropriateness. The interview coding process will parallel that described in Aim 1. We will use an integrated deductive and inductive coding approach. Transcripts will be reviewed using deductive methodology, where CFIR determinants will be used as the coding framework. After completion, the transcripts will be re-reviewed using inductive methodology where codes identifying novel barriers and facilitators of implementation that do not map onto the CFIR will be identified and used to develop a coding framework that is then applied to all transcripts. We will integrate the qualitative and quantitative data by merging findings through a comparative coding analysis. The AIM and FIM scores will be dichotomized (completely disagree/disagree vs completely agree/agree). We will compare the distribution of content themes between providers with high vs low acceptability and, separately, high vs low feasibility ratings. Data will then be used as a starting point in which to build an optimized PrEP-inclusive coaching implementation strategy to be tested in the subsequent RCT.

Aim 3: The primary analysis will be based on an intention to treat approach and will include all subjects randomized at Visit 1.

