The primary outcome for the RCT is the change in prevention self-efficacy between intervention and control conditions between the baseline and six-month (final) visits. We will compare the exposure variable of treatment group with the outcome variable of continuous score on the modified Generalized Self-Efficacy Scale at baseline, intermediate (e.g. three month), and six-month visits using mixed effects logistic regression models with a random intercept for patient and a random slope for time. In exploratory analyses, to determine if the mental health predictors impact the self-efficacy outcome, we will create separate mixed effects regression models to compare self-efficacy score for those with and without mood ratings consistent with depression on the PSC-17, high trauma (Adverse Childhood Experiences Scale score >4 vs not), and substance abuse (CRAFFT score >4) adjusting for treatment group and demographic characteristics including sex. In order to assess the impact of STI timing on the primary outcome of prevention self-efficacy, we will use linear regression models and days between STI diagnosis and the first coaching visit in the intervention group, adjusting for demographic covariates including sex and sexual orientation. Finally, we will assess if coaching may have a significant effect on other domains in the self-efficacy pathway of our model, by repeating the primary analysis above with scores for the Patient Activation Measure [PAM], and Confidence in Safer Sex Scale.

There will be no adjustment of p value for multiple comparisons given the exploratory nature of these analyses.

Secondary outcome analyses:

- Referral feasibility: Calculated as the number of potential participants referred to study staff over the number of patients with bacterial STI at the clinics during the study period. This denominator will be identified using the CHOP STI dataset.
- Recruitment feasibility: Calculated as the number of patients enrolled over the number of patients referred.

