6.4 Sample Size and Power

Aim 1: The individual focus group size of 5-8 is informed by consensus methods literature. The goal of the pooled focus group size of ~50 is thematic saturation. The goal of the in-depth interviews is thematic saturation, which could be reached at ~15 participants. If we do not reach saturation at this sample size, or if key themes emerge among subgroups of participants which we wish to further explore, we will continue focus groups and in-depth interviews until saturation is met.

Aim 2: Previous studies demonstrate that 3-6 charts per clinician are sufficient for reliable and valid assessment in CSRs. We propose to interview 25 clinicians and nurses with the goal of achieving saturation of themes, for which this sample size should be sufficient, and will continue if saturation is not met.

Aim 3: We propose a sample size of 150 participants (75 intervention, 75 control – with the possibility of a greater number of intervention than control if we shift to 2:1 randomization) based on the aim of detecting a moderate effect size score difference in the change in modified GSES scores between intervention and control. Given this sample size, and assuming a range of intra-subject correlations across subjects ranging from (0.01 to 0.3), we will have 80% power and a two-sided alpha of 0.05 to detect a 0.7-0.9 standard deviation difference change in GSES scores from baseline and six months by treatment group. And be protected from and up to 10% lost-to-follow-up rate.

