9 STUDY ADMINISTRATION

9.1 Treatment Assignment Methods

9.1.1 Randomization

Aim 3: Simple 1:1 randomization will occur at baseline using the REDCap randomization tool. The randomization tables will be created by a statistician that is not a part of the study team. The study team will not take part in randomization. Participants will complete the baseline CASI before being randomized. The study team will not be able to change randomization after it is applied in REDCap.

As mentioned in Section 3, if difficulty retaining coaching participants during the RCT generates a disparity in evaluable participants per arm, the RCT's randomization scheme will be changed to 2:1, intervention vs SOC, to balance numbers of evaluable participants per arm.

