9.7 Payment to Subjects/Families

Aim 1: The participants in Aim 1 will receive \$40 in total for their participation in the study. After completing the CASI at time of enrollment, they will receive \$10 and then will receive \$30 once they complete the focus group or in-depth interview.

Aim 2: The participants in Aim 2 will receive \$20 for their participation in the study.

Aim 3: Participants in both arms of the RCT will receive \$40 each at the baseline visit, the three-month visit and the six-month follow up visit. Participants who complete baseline surveys within 3 business days of link receipt will receive \$10. Participants in the health coaching arm of the RCT will receive an additional \$5 if they complete a feedback survey in REDCap after the 1-week coaching session, and they will receive an additional \$5 if they complete a feedback survey in REDCap or a feedback interview after the 3-month coaching session. At the 3-month time point, participants in the health coaching arm who completed a baseline coaching session but have missed subsequent visits, including a missed 3-month coaching session, will be offered \$15 compensation for completing a feedback survey in REDCap.

Compensation will be paid using the ClinCard system. As per CHOP guidelines, all subjects will need to provide their contact information in order to process their ClinCard. They will also need to sign and date the ClinCard Compensation Receipt (CCR) as proof of receipt of their ClinCard as study payment, except for those participants who complete a visit by phone. Participants who complete a visit by phone or video conferencing will receive a ClinCard via mail. A member of the research team will contact them to confirm receipt of the ClinCard before loading any funds onto their card.

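### Section 6.3.2 leaves the time, treatment-by-time and baseline terms of the primary GSES model open; fixing a common baseline mean in a linear model would gain precision at almost no cost

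*Combined protocol and SAP*

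**What the plan says.** Section 5.2 sets the target: "The primary efficacy outcome is the difference in change in self-efficacy between baseline and six-month visits for the intervention group versus control". Section 6.3.2 repeats it and specifies the model. Treatment group is the exposure. The outcome is the "continuous score on the modified Generalized Self-Efficacy Scale at baseline, intermediate (e.g. three month), and six-month visits using mixed effects logistic" regression, "with a random intercept for patient and a random slope for time". Baseline GSES is therefore one of the outcome rows. The analysis is by intention to treat and "will include all subjects randomized at Visit 1".

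No section adds a fixed time term, a treatment-by-time term, the coding of time (categorical or linear), or a rule for baseline. The covariates named in 6.3.2 belong to the exploratory and STI-timing models.

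Section 6.4 gives 75 per arm, 80% power, two-sided alpha 0.05 and up to 10% loss, "assuming a range of intra-subject correlations across subjects ranging from (0.01 to 0.3", and says this is enough "to detect a 0.7-0.9 standard deviation difference change in GSES scores". Section 9.1.1 states: "Participants will complete the baseline CASI before being randomized".

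**The concern.** Two analysts could follow section 6.3.2 faithfully and report different primary estimates. One would give each arm its own baseline mean, so that the treatment effect is the between-arm difference in change. The other would fit one baseline mean for both arms, as randomisation after the baseline survey justifies. Both target the quantity in section 5.2, but their precision differs, and the difference is greatest at the low correlations that section 6.4 assumes. Allocation is open (section 9.1.2), so the choice should be fixed in advance.

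Logistic is also the wrong family for a continuous score. That is a separate error, and none of the figures below depends on it; they all assume a linear model.

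**Working it through.** **Inputs.** From section 6.4: 75 per arm, 10% loss (67.5 per arm at six months), two-sided alpha 0.05, correlation ρ from 0.01 to 0.3, effect 0.7 to 0.9 SD. The plan does not define the correlation; I read it as baseline to six months. It gives no SDs. I set the baseline SD to 1 and the six-month SD to s, with s = 1.0 or 1.3. The 1.3 is my assumption.

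**The plan's own figure.** Detectable change difference = (1.960 + 0.842) × √[2(1−ρ)] × √(2/n).
- n = 75: 0.64 SD (ρ = 0.01) to 0.54 SD (ρ = 0.3).
- n = 67.5: 0.68 to 0.57 SD.

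The stated 0.7-0.9 SD is not reproduced. That is a separate matter and does not enter the comparison below.

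**Complete data.** Write the variance of the six-month contrast as v × (1/n₁ + 1/n₂).
- Free baselines: v = 1 + s² − 2ρs
- Common baseline: v = s²(1 − ρ²)
- Power at effect d ≈ Φ(d/SE − 1.96). Example: v = 1.98 and n = 67.5 give SE = √(1.98 × 2/67.5) = 0.242, so 0.7/0.242 = 2.89 and power is Φ(0.93) = 82%.

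| s | ρ | v free | v common | Reduction | Power at 0.7, free | Power at 0.7, common |
|---|---|---|---|---|---|---|
| 1.0 | 0.01 | 1.980 | 1.000 | 49.5% | 82.4% | 98.2% |
| 1.0 | 0.3 | 1.400 | 0.910 | 35.0% | 93.0% | 98.9% |
| 1.3 | 0.01 | 2.664 | 1.690 | 36.6% | 70.2% | 87.9% |
| 1.3 | 0.3 | 1.910 | 1.538 | 19.5% | 83.7% | 90.6% |

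With equal SDs, six-month scores alone have v = 1.00. The change contrast is therefore noisier than ignoring baseline at every correlation in the plan's range.

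At s = 1.3 the free-baseline power is 74% at ρ = 0.1 and 79% at ρ = 0.2, and it reaches 80% at about ρ = 0.22. It is below 80% over most of the plan's range. At 0.9 SD it is 96-99% (s = 1.0) or 89-97% (s = 1.3).

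**10% loss, baseline rows kept in both models.** Per arm, with n = 75 baselines and m = 67.5 six-month values:
- Free: s²(1−ρ²)/m + (ρs−1)²/n
- Common: s²(1−ρ²)/m

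Example, s = 1 and ρ = 0.01: 0.9999/67.5 + 0.9801/75 = 0.01481 + 0.01307 = 0.02788, against 0.01481. The reduction is 46.9%. The other cases are 32.6% (s = 1, ρ = 0.3), 34.2% (s = 1.3, ρ = 0.01) and 17.9% (s = 1.3, ρ = 0.3). With equal SDs the detectable difference falls from 0.66 to 0.48 SD at ρ = 0.01, and from 0.56 to 0.46 SD at ρ = 0.3. Adding the three-month data changes these reductions by about 0.1 point.

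**Higher correlation, complete data.** With equal SDs the gain is 25% at 0.5, 15% at 0.7 and 5% at 0.9. At s = 1.3 it is 9% at 0.5 and 1% at 0.7. It is zero where ρs = 1 (ρ = 1/1.3 = 0.77), and about 8% at 0.9.

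**The plan's own random effects.** With intercept variance 0.3, slope variance 0.69 over the six months and residual variance 0.7 (all assumed), v is 2.090 against 1.600. The reduction is 23.4%, and power at 0.7 is 80.3% against 89.5%.

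**2:1 allocation.** If it applied throughout (90/45 evaluable, equal SDs), power at 0.7 is 78-90% against 97-98%. If 75 are randomised 1:1 and 75 at 2:1, with an assumed 0.3 SD drift in level between periods, a common baseline without period terms is biased by 0.051 SD (ρ = 0.01) or 0.036 SD (ρ = 0.3). With period terms the bias is zero, and the variance rises from 0.0274 to 0.0282 (about 3%) at ρ = 0.01.

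**The case against.** The sponsor can say that treatment is named as the exposure and that a difference in change implies a treatment-by-time term, so it would be wrong to infer that no fixed effect is given. That stands. What is missing is the explicit time and interaction terms and the treatment of baseline.

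The loss depends on a model that the plan does not state. If the intended model has no treatment term at baseline, the gain is already taken. That also stands, but the text does not show it. The stated random slope may mean linear time; the gain with 10% loss is then larger (39-58% with equal SDs, 26-49% at s = 1.3).

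A reader might infer that the trial is underpowered. The documents do not support that. With equal SDs and 1:1 allocation, even the free-baseline contrast has at least 82% power at 0.7 SD. If section 6.4's SD is the SD of change, power at 0.7 is 98% at any correlation. A shortfall at 1:1 appears only with the assumed SD ratio.

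A reader might also infer a conflict over whether the baseline survey precedes allocation. Table 1 and section 4.1 list randomisation above the survey, and section 9.7 pays "Participants who complete baseline surveys within 3 business days of link receipt". The lists need not be chronological, and prompt-completion pay is compatible with section 9.1.1, which is explicit. There is no contradiction.

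Finally, a free-baseline mixed model also retains everyone with baseline data, so retention is no argument for the change. The free-baseline contrast also avoids the drift bias after a switch to 2:1. Both points stand, and the second is why the fix needs period terms.

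**Conclusion.** The concern holds as a gap in specification with a cost in precision. Section 6.3.2 leaves the primary estimator open. If arm baselines are free, a common-baseline linear model has 47% to 33% lower variance with equal SDs, or 34% to 18% at an SD ratio of 1.3. These figures assume categorical visits, 10% loss with baseline rows kept, and section 6.4's 0.01-0.3 as the baseline-to-six-month correlation. With complete data, 67.5 per arm and 0.7 baseline SD, power is 82-93% against 98-99%, or 70-84% against 88-91% at ratio 1.3. The gain shrinks with rising correlation when SDs are equal; at ratio 1.3 it vanishes near 0.77 and then rises slightly.

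It would be wrong to read this as bias or as a breach of intention to treat: both estimators target the section 5.2 contrast. The change should be made, but the trial's validity does not hang on it.

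**What to change.** In section 6.3.2:
- Replace the logistic model with a linear mixed model for GSES at all three visits.
- Make visit categorical, with a common baseline mean across arms and treatment-by-visit terms at three and six months.
- State the covariance: keep the random intercept and slope, or replace them with an unstructured covariance.
- Name the six-month treatment contrast as primary.
- If allocation switches to 2:1 (sections 3.2 and 9.1.1), add randomisation-period and period-by-visit terms, because the common baseline mean then holds only within period.

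The cost is SAP wording. Baseline GSES is already collected in both arms before randomisation, and the model has one parameter fewer than the free-baseline version. If 2:1 is used, the three period terms raise the variance by about 3%.

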- Retention feasibility: Calculated as the proportion of participants who completed each follow-up coaching session over the total number of scheduled coaching visits. To determine if the mental health is associated with retention, I will use logistic regression to compare proportions of subjects retained between the following participant groups: high depressive symptoms, high trauma score, and substance abuse (see definitions in exploratory analysis section above), adjusting for demographic characteristics such as race and sex.

Fidelity will be assessed by reviewing baseline visit transcripts for the first ten participants and reviewing a random sample of 2 visits per week for ongoing supervision

- We will use the Motivational Interviewing Assessment-Supervisory Tools for Enhancing Proficiency (MIA-STEP) cut offs for fidelity: interventionist will have to demonstrate in the first ten sessions the use of at least half of the MI consistent items three to four times, namely, receive a “Somewhat” (4) frequency and extensiveness rating and at least an “Adequate” (4) skill level rating. In other words, the interventionist has to show capacity to use a moderate amount of MI strategies and skills and show an adequate level of performance when implementing them.
- On random sample, if three successive sessions occur in which they fall below proficiency standards, the interventionist will receive additional training, feedback, and coaching until he or she demonstrated again the minimal MI proficiency standards. Supervisors may elect to use the protocol’s MI proficiency standards as a supervisory benchmark for their clinicians. The MIA-Step MI rating worksheet tool (see below) will be used to assist in this task (<https://motivationalinterviewing.org/sites/default/files/mia-step.pdf>)
- In addition, the interventionist will complete the content checklist after each visit to assure each psychoeducation content domain (e.g. condoms, partner notification) was addressed in the session.
- Acceptability: I will calculate the proportion of participants who endorse each item on the Coaching Satisfaction Survey in the "agree" or "strongly agree" range.

Exploratory outcome analyses: Utilization of prevention behavior at the six-month time point. I will calculate the proportion of participants who:

- Initiate PrEP
- Do not develop repeat sexually transmitted infection (STI)
- Report 100% condom use
- Receive HIV testing
- Report partner notification of their initial STI

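### The primary analysis names mixed-effects logistic regression for a GSES score that the plan calls continuous, defines as a change and sizes in standard deviations

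*Combined protocol and SAP*

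**What the plan says.** Section 6.3.2 (Aim 3) takes as its response the "outcome variable of continuous score on the modified Generalized Self-Efficacy Scale at baseline, intermediate (e.g. three month), and six-month visits" and analyses it "using mixed effects logistic regression models with a random intercept for patient and a random slope for time". Both phrases are in one sentence.

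Other parts of the plan bear on how to read it:

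- Section 5.2 defines the target: "The primary efficacy outcome is the difference in change in self-efficacy between baseline and six-month visits for the intervention group versus control". Section 6.3.2 describes the primary outcome in the same terms.
- Section 6.4 sizes the trial to detect a difference of 0.7 to 0.9 SD in GSES change. It assumes 150 participants (75 per arm), 80% power, two-sided alpha 0.05, intra-subject correlation 0.01 to 0.3 and up to 10% loss.
- Two neighbouring analyses of the same score do not use the word *logistic*: "we will create separate mixed effects regression models to compare self-efficacy score" and "In order to assess the impact of STI timing on the primary outcome of prevention self-efficacy, we will use linear regression models".
- Logistic regression does appear where the outcome is binary, for retention: "I will use logistic regression to compare proportions of subjects retained between the following participant groups".
- The only scores that the plan says it will dichotomise belong to Aim 2: "The AIM and FIM scores will be dichotomized (completely disagree/disagree vs completely agree/agree".
- The primary model is reused for two more scales, "by repeating the primary analysis above with scores for the Patient Activation Measure [PAM], and Confidence in Safer Sex Scale".

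**The concern.** A logistic model needs a binary or ordered-category response. The plan gives neither for the GSES, so the primary model cannot be run on the stated outcome. An analyst must either depart from the written model or invent a cut-point or an ordinal coding. Section 6.3.2 is the only analysis specification in the document, and Sections 3.2 and 9.1.2 leave the study team unblinded. That choice would therefore be made by people who can see the allocation, possibly after data have accrued.

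Following the word would also change what is estimated. An odds ratio is not a difference in mean change and cannot be compared with the 0.7 to 0.9 SD that justified the sample size. Cutting the score discards information and costs power.

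A smaller gap sits in the same sentence: it does not list the fixed effects or name the treatment-by-time term that carries the target. That is incomplete specification rather than contradiction, because Sections 5.2, 6.3.2 and 6.4 all state the target.

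**Working it through.** The contradiction is textual and needs no arithmetic. The figures below show what each reading would cost.

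**Inputs from Section 6.4.** 75 per arm less 10% gives 67.5 evaluable per arm; two-sided alpha 0.05; correlation ρ from 0.01 to 0.3; difference in change 0.7 to 0.9 SD. The section does not say whether SD means that of a single score or of the change. The single score is taken first.

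**The plan's own figure.** With a score SD of 1, the variance of a change is 2(1−ρ), and the standard error of the difference in change is √[2(1−ρ)(1/n₁+1/n₂)].

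- ρ = 0.01: √[1.98 × 2/67.5] = 0.2422; detectable difference at 80% power (noncentral t) 0.684 SD.
- ρ = 0.3: √[1.40 × 2/67.5] = 0.2037; detectable difference 0.575 SD.

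The stated 0.7 to 0.9 is therefore not reproduced; only its lower end is approached. In SD-of-change units the detectable difference is 0.46 at 75 per arm and 0.48 at 67 per arm. The plan's range is larger than either calculation gives. That is a separate matter and does not affect the point here.

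**Linear contrast, true difference 0.7 score SD.** Power is 0.818 (ρ = 0.01) and 0.927 (ρ = 0.3).

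**Logistic by cutting the score.** The cut is an assumption, because the plan gives none. Baseline and six-month scores are taken as bivariate normal with SD 1, no change in control and a rise of d in intervention. The estimate is the between-arm difference in change of log-odds of exceeding the cut. Each arm contributes variance [1/(p₀q₀) + 1/(p₁q₁) − 2·cov/(p₀q₀p₁q₁)]/n, where p₀ and p₁ are the proportions above the cut at baseline and six months, q = 1 − p, and cov is the within-patient covariance of the two indicators. This is a two-visit marginal approximation to the logistic treatment-by-time term.

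At the baseline median with d = 0.7, the intervention arm moves from 0.500 to Φ(0.7) = 0.758 above the cut. The log odds ratio is ln(0.758/0.242) = 1.142 (odds ratio 3.13). At ρ = 0.01 the standard error is 0.507, so power is Φ(1.142/0.507 − 1.96) ≈ 0.615. At ρ = 0.3 the standard error is 0.460 and power is 0.700. A simulation of 20,000 trials with 68 and 67 per arm gave 0.623 and 0.720.

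| Cut (SD from baseline median), d = 0.7 | Odds ratio | Power, ρ = 0.01 | Power, ρ = 0.3 |
|---|---|---|---|
| 0 | 3.13 | 0.615 | 0.700 |
| +0.5 | 3.09 | 0.586 | 0.670 |
| −0.5 | 3.43 | 0.547 | 0.617 |
| +1 | 3.28 | 0.473 | 0.537 |
| −1 | 4.04 | 0.396 | 0.436 |

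**Sensitivity to effect size and SD unit** (67.5 per arm; ρ = 0.01 and 0.3):

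| True difference | Linear | Median cut |
|---|---|---|
| 0.7 score SD | 0.82, 0.93 | 0.62, 0.70 |
| 0.9 score SD | 0.96, 0.99 | 0.81, 0.88 |
| 0.7 SD of change | 0.98, 0.98 | 0.87, 0.83 |

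In the last two rows, cuts 0.5 to 1 SD from the median give 0.51 to 0.86. An ordinal logistic model, which the plan does not name either, was not quantified.

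**Why the contrast should be named.** If the arms diverge linearly, the treatment effects at the three visits are 0, 0.5d and d. With equal correlations and complete data, a treatment main effect over all three visits estimates their mean, (0 + 0.5 + 1)d/3 = 0.5d. The treatment-by-time term, taken to six months, estimates d.

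**The case against.** The strongest reply is that this is a one-word slip that the document resolves. The score is called continuous, the outcome is a change, the sizing is in SDs, the same outcome is analysed by linear regression a few lines later, and logistic regression is elsewhere kept for a proportion. The software would expose the error on the first run, and harm requires an analyst to override the word *continuous*. The plan also describes a small RCT meant to lead to a fully powered one. All of that is fair, and *linear* is very likely what was meant. It does not remove the need to correct the text: this is the model for the only primary endpoint of the RCT, and two further analyses are defined by repeating it.

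The second reply is that power of 40% to 72% describes only the bottom of the plan's effect range under one reading of SD. That stands. At 0.9 score SD, or at 0.7 SD of change, a median cut keeps more than 80% power. The size of the loss depends on the effect, the SD unit and the cut. In every scenario computed, though, the cut score has less power than the linear contrast.

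The third reply is that no reader of Section 5.2 would report a treatment main effect. That also stands: leaving the treatment-by-time term unnamed is a lesser point that adds nothing to the case against the word *logistic*.

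**Conclusion.** The concern holds on the text alone. The primary model does not match the type of outcome, the stated target or the scale of the sample size, and it must be corrected before analysis. If the word were followed by a median cut, power at 0.7 score SD would fall from 82% to about 62% (ρ = 0.01) and from 93% to 70–72% (ρ = 0.3). Cuts 0.5 to 1 SD from the median would leave 40–59% and 44–67%. The same 0.7 SD effect would appear as an odds ratio anywhere from 3.1 to 4.0 depending on the cut. The loss is smaller at larger effects or if SD means SD of change.

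These figures assume normal scores, 1:1 allocation, 10% loss in each arm, a two-visit approximation and cut-points that the plan does not supply. They illustrate the consequence; the finding does not depend on them.

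**What to change.** In the primary analysis sentence of Section 6.3.2, replace *logistic* with *linear* and complete the specification: a linear mixed model for the GSES score with fixed effects for treatment, time and treatment-by-time, keeping the random intercept and slope already named. State that the primary estimate is the treatment difference in change from baseline to six months, with its 95% confidence interval. Coding visit as categorical is optional. The correction then carries to the Patient Activation Measure and Confidence in Safer Sex analyses.

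If a binary or ordinal analysis really is intended, state the cut-point or categories now and redo the sample size on that scale.

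The cost is an amendment to wording, with no new data. Under 1:1 allocation with 10% loss, the linear contrast keeps at least 80% power at 0.7 SD over the stated correlations, on either reading of SD, so the correction does not call for a larger sample.

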6.2 Secondary Endpoints

Aim 1: None

Aim 2: None

Aim 3:

- Referral feasibility: # potential participants referred/# eligible.
- Recruitment feasibility: # enrolled/# patients referred.
- Retention feasibility: # completing all sessions/# enrolled.
- Acceptability: Assessed at the final visit by a Coaching Satisfaction Survey
- Secondary outcomes:
 - a) Repeat STI test results at three-months and six-months.
 - b) Prevention behavior, including uptake of PrEP, condom use, HIV testing, and partner notification of positive STI results

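### The retention models have no sparse-data method although the expected number of non-completers is unknown; Firth-penalised logistic regression in the coaching arm would be a cheap safeguard

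*Combined protocol and SAP*

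**What the plan says.** Section 6.3.2 (Aim 3, secondary outcome analyses) sets out the model: "I will use logistic regression to compare proportions of subjects retained between the following participant groups". It compares participants with and without high depressive symptoms, high trauma score and substance abuse, and adjusts for demographic characteristics, with race and sex as examples. It names no penalised or exact method, no limit on covariates and no rule for small categories.

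Retention is defined twice. Section 6.2 has "Retention feasibility: # completing all sessions/# enrolled". Section 6.3.2 has "Calculated as the proportion of participants who completed each follow-up coaching session over the total number of scheduled coaching visits". Both rest on sessions, and under section 4.2 the standard-of-care arm receives no coaching during the trial.

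The only attrition figure is in section 6.4, attached to the power statement for the modified Generalized Self-Efficacy Scale (GSES): "And be protected from and up to 10% lost-to-follow-up rate". Sections 3.1, 3.2 and 9.1.1 foresee possible difficulty in retaining coaching participants and allow a switch to 2:1 randomisation. No section gives an expected session-completion rate, the prevalence of the three mental-health groups, or the number of race categories.

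**The concern.** A logistic model is limited by its rarer outcome, here the participants who do not complete coaching. If a group or covariate level contains no non-completers, or only non-completers, maximum likelihood has no finite estimate for that coefficient. Software then prints a very large odds ratio with a meaningless standard error, or drops the level and its participants. An arm of about 75, several covariates and an unknown event count leave room for this. Because the plan has no stated answer, any fallback would be chosen after the data are seen.

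The stake is modest but real. Whether youth with depressive symptoms, trauma or substance abuse leave coaching is a planned secondary question, and section 10 says the trial will support an application for a larger one.

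**Working it through.** **Plan's own figure.** There is none for the retention model. The 10% belongs to the GSES calculation, "we will have 80% power and a two-sided alpha of 0.05 to detect a 0.7-0.9 standard deviation difference change in GSES scores", with "assuming a range of intra-subject correlations across subjects ranging from (0.01 to 0.3". In baseline-SD units, the SD of change at correlation 0.01 is √(2 × 0.99) = 1.41. For 0.7 SD, n per arm = 2 × (1.96 + 0.84)² × 1.98 / 0.49 ≈ 64, and 64 / 0.9 ≈ 72, close to the 75 planned. So the 10% acts as an inflation of the GSES sample size. The 0.9 SD end is not reproduced this way; that is a separate matter.

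**Inputs from the plan.** Size: "We propose a sample size of 150 participants (75 intervention, 75 control". Coaching sessions are at baseline, 1 week, 1 month and 3 months, so there are three follow-up sessions, or four in all.

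**Assumptions, not in the plan.** Non-completion 10% to 40%; group prevalence 15% to 30%; true odds ratio 2; sex 40/60; race in two groups or four (for example 70/15/10/5%).

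**Step 1: events in the coaching arm.**
- At 10%: 0.10 × 75 = 7.5. If all 150 were randomised 2:1, 0.10 × 100 = 10.
- If each visit is missed independently with probability 10%, non-completion is 1 − 0.9³ = 27% over three sessions (about 20 of 75) or 1 − 0.9⁴ = 34% over four (about 26).
- At 40%: 0.40 × 75 = 30.

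**Step 2: events per coefficient.** One mental-health group, sex and two-level race make three coefficients; four-level race makes five.
- At 10%: 7.5/3 = 2.5 and 7.5/5 = 1.5.
- At 27%: 20/3 = 6.7 and 20/5 = 4.0.
- At 40%: 30/3 = 10 and 30/5 = 6.

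**Step 3: chance of an infinite mental-health odds ratio, by hand.** The main route is an exposed group with no non-completers, with probability (1 − p₁)^m, where m is the number exposed and p₁ their non-completion risk.
- 10% overall, odds ratio 2, prevalence 15%: m = 11.25, p₁ = 0.163, so 0.837^11.25 ≈ 0.13.
- 10% overall, odds ratio 2, prevalence 30%: m = 22.5, p₁ = 0.1475, so 0.8525^22.5 ≈ 0.03.
- 27% overall, odds ratio 2, prevalence 15%: p₁ = 0.397, so 0.603^11.25 ≈ 0.003.
- With no true association the risk is higher. For 7 or 8 events in 75, the exact hypergeometric probability is 26-31% at 15% prevalence and 5-8% at 30%.

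**Step 4: adjusted model, by simulation (odds ratio 2, n = 75).**

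| Non-completion | Mental-health odds ratio infinite | Any coefficient non-finite, four race groups |
|---|---|---|
| 10% | about 3-15% | close to 90% |
| 27-40% | 0-2% | roughly 30-50% |

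For the same data sets, Firth estimation gave a root-mean-square error for the mental-health log odds ratio about 7-30% lower in every setting, without loss of interval coverage. Its estimates are finite by construction.

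**Step 5: precision when the estimate is finite.** SE(log OR) = √(1/a + 1/b + 1/c + 1/d) on expected cell counts. With 8 events and 30% prevalence the cells are 2.4, 5.6, 20.1 and 46.9, so SE = 0.82 and the 95% interval is the odds ratio multiplied and divided by exp(1.96 × 0.82) ≈ 5. With 7 events and 15% prevalence the factor is about 9. With 20 events it is about 3.1-4.2.

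**The case against.** The strongest reply is that the sparse case may never arise. The section 6.4 figure, "up to 10% lost-to-follow-up rate", is a ceiling on loss to follow-up for another outcome. Section 3.1.3 lets a coaching participant attend the 6-month visit after a single coaching session, so missing sessions is not loss to follow-up. The plan itself anticipates poor coaching retention, which would mean more events. This stands. A reader might infer that the plan implies 15 events among 150 participants, but the documents do not support that: the 10% is not a retention rate, and controls have no coaching sessions to complete.

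A second reply is that the instability lies mainly in race coefficients that nobody will interpret, under a race split the documents do not give. That also largely stands. When only a race level separates, the mental-health odds ratio stays finite. Collapsing race levels with fewer than 10 participants, with ordinary maximum likelihood, leaves a non-finite coefficient in only about 0.5-2.5% of data sets at 27-34% non-completion. At 10% it leaves 28-39%, still mostly in race or sex coefficients.

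Third, Firth adds no events, and the outcome must be defined first. If it were analysed session by session, observations would be clustered within participants and a participant-level Firth model would not deal with that. This stands too, and it sets the order of the fix.

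What remains is that the event count cannot be known in advance and the plan has no stated answer if it is small.

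**Conclusion.** The point holds as a minor improvement. The retention models lack an expected event count, a stated analysis population and a sparse-data method. At 10% non-completion the coaching arm would have 7-8 events, and the mental-health odds ratio would be infinite in about 3-15% of data sets; at 27-40% it would have about 20-30 events and 0-2%. These figures assume a true odds ratio of 2 and prevalences of 15-30%; with no association and a 15% prevalence the risk at 7-8 events is nearer 30%.

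A reader might go further and infer that the estimates will often be infinite and the question will go unanswered. The documents do not support that. They fix neither the event rate nor the race coding, and at the higher non-completion rates the mental-health estimate is nearly always finite, with Wald coverage near or above nominal. The analysis is a secondary feasibility one, and the GSES comparison is untouched.

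**What to change.** In section 6.3.2, in this order:

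1. State one participant-level definition of retained, reconciled with section 6.2, and name the coaching arm as the analysis population.
2. Fit each retention model by Firth penalised-likelihood logistic regression with profile-likelihood intervals.
3. List the adjustment covariates and set in advance a rule for collapsing sparse race levels, for example those with fewer than 10 participants.
4. Next to each odds ratio, report the unadjusted difference in retention with a score or exact interval.

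The cost is a few sentences and a standard software option. The downside is slight shrinkage of odds ratios towards 1. Intervals will stay wide, because the method adds no information. If events turn out to be plentiful, the Firth and ordinary estimates will nearly coincide and little is lost.
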